5.2 Exclusion Criteria

Subjects are excluded from the study if any of the following criteria apply:

1. History of, or current signs and symptoms of, diseases or conditions that would make participation not be in the best interest (eg, compromise the well-being) of the subject or that could prevent, limit, or confound the protocol-specified assessments.
2. History of moderate or severe head trauma (for example, loss of consciousness for more than 15 minutes) or other neurological disorders (including a diagnosis of epilepsy or has had a seizure in the last 6 months), neurodegenerative disorder (Alzheimer's disease, Parkinson's disease, multiple sclerosis, Huntington's disease, etc.) or systemic medical diseases that are, in the opinion of the Investigator, likely to interfere with the conduct of the study or confound the study assessments. A history of febrile seizures in childhood is not exclusionary.
3. Has a primary DSM-V diagnosis of current (active) MDD with psychotic features, panic disorder, obsessive compulsive disorder, posttraumatic stress disorder, anorexia nervosa, or bulimia nervosa. Comorbid anxiety or panic disorder that does not dominate the clinical presentation is acceptable.
4. Has a current or prior DSM-V diagnosis of a primary psychotic disorder (eg, schizophrenia), bipolar or related disorders (confirmed by the MINI), intellectual or autism spectrum disorder, or borderline personality disorder.
5. Has any significant disease or disorder (eg, cardiovascular, pulmonary, gastrointestinal, hepatic, renal, neurological, musculoskeletal, endocrine, metabolic, malignant, psychiatric, major physical impairment) that, in the opinion of the Investigator, may either put the subject at risk because of participation in the study, influence the results of the study, or affect the subject's ability to participate in the study.
6. Has uncontrolled hypertension, despite medication, at Screening (systolic blood pressure [SBP] > 160 mm Hg or diastolic blood pressure [DBP] > 90 mm Hg) or any past history of hypertensive crisis. An abnormal blood pressure value at screening may be repeated once after 10-15 minutes of relaxation to determine the subject's eligibility.
7. Has an abnormal ECG of clinical relevance at screening or baseline (Day -1) including, but not limited to, the following:

- QT interval corrected according to Fridericia's formula (QTcF) interval > 450 msec for male subjects and >470 msec for female subjects.

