In the case where a second (repeat) measurement was taken for a particular timepoint, only the second (repeat) measure will be included for analysis and the first measure will not be analyzed.

For the following 12-lead ECG parameters, summaries of values and its changes from baseline will be presented by treatment group for each scheduled assessment timepoint, beginning with the Baseline visit.

- Heart rate
- PR interval
- QRS interval
- QT interval (uncorrected)
- QT interval corrected with Fridericia's formula (QTcF)

A separate summary table will provide the number and percentage of subjects meeting the following criteria post-baseline. For this analysis, any ECG performed on unscheduled analysis visits will be included for analysis. However, any initial measurement which was superseded by a repeat measurement within the same analysis timepoint would NOT be included for this analysis.

- Absolute QTcF interval prolongation:
 - QTcF interval \geq 450 msec
 - QTcF interval \geq 480 msec
 - QTcF interval \geq 500 msec
- Change from baseline in QTcF interval:
 - QTcF interval increase from baseline \geq 30 msec

- QTcF interval increase from baseline \geq 60 msec

In the case where a subject reports qualifying records (ie, ignoring superseded initial readings) of both Abnormality with Clinical Significance and Abnormality without Clinical Significance at different analysis timepoints in a post-baseline period, the most severe record (ie, abnormality with clinical significance) will be selected for summarization.

A listing of all ECG measures will be presented.

H. Prior and Concomitant Therapy

Concomitant therapy is defined as any therapy with a start date after or on the date of the study treatment and continuing after the study treatment (ie, including up to the second follow-up visit or ongoing). Any therapy with a start date after the second follow-up visit will not be considered a concomitant therapy.

Any therapy which started prior to the infusion of study treatment is defined as a *prior* therapy. For the imputation of missing therapy dates in the categorization of prior vs concomitant status, refer to [Section XI.A Missing or Partial Date Imputation](#).

Concomitant medications will be coded using World Health Organization (WHO) Drug version September 2020 or higher coding dictionary and will be summarized by the anatomical main class (1st level) of each coded medication and, within that, the preferred name of the coded medication.

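### The lowest absolute QTcF row in SAP VIII.G (450 msec or more) counts women who were eligible at 450 to 470 msec and did not change as prolonged; add a baseline count and a treatment-emergent row

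*SAP*

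**What the plan says.** Protocol 5.2, exclusion 7 (repeated in the synopsis), removes subjects with "QT interval corrected according to Fridericia's formula (QTcF) interval > 450 msec for male subjects and >470 msec for female subjects". The limit applies at screening and at Day -1. Because it is a strict inequality, women up to and including 470 msec and men up to and including 450 msec may enrol.

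SAP VIII.G plans one categorical QTcF table: "A separate summary table will provide the number and percentage of subjects meeting the following criteria post-baseline". Under "Absolute QTcF interval prolongation" it lists three cut-offs, the lowest being "QTcF interval \geq 450 msec", then 480 and 500 msec. Under "Change from baseline in QTcF interval" it lists increases of at least 30 and at least 60 msec. Unscheduled ECGs count, but "any initial measurement which was superseded by a repeat measurement within the same analysis timepoint would NOT be included for this analysis". No cut-off is split by sex, and no absolute row requires a baseline below the cut-off.

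SAP V.B defines baseline as the last evaluable value before dosing. For ECG this is normally the Day 1 predose recording in the protocol's Schedule of Activities. No ECG shift table is planned. For laboratory data, SAP VIII.D does restrict its shift tables to subjects who were normal at baseline.

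**The concern.** The entry rule and the counting rule overlap. Women from 450 to 470 msec, and a man at exactly 450 msec, satisfy both. Such a subject enters the row labelled prolongation even if the infusion changes nothing, and the row gives no way to separate her from a subject who crossed 450 msec after dosing.

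One subject is 1/31 = 3.2 percentage points of an arm, so one or two carried-in values change the printed rate visibly. Randomization is stratified by region only (SAP III.D), so the arms may differ by chance in the number of women or in baseline QTcF. The change-from-baseline rows are separate counts and do not show which subjects in the 450 msec row started there. The SAP already conditions on baseline for laboratory shifts, and its definition of treatment-emergent adverse events also requires onset or worsening after the start of infusion. This ECG row does neither.

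**Working it through.** The documents state no figure for this point, so there is none to reproduce. The first step is logical. The second and third rest on assumed values.

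**1. Entry rule against counting rule, QTcF unchanged after dosing**

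| QTcF (msec) | Woman eligible | Man eligible | Counted in 450 row | Counted in any other row |
|---|---|---|---|---|
| 449 | yes | yes | no | no |
| 450 | yes | yes | yes | no |
| 455 | yes | no | yes | no |
| 460 | yes | no | yes | no |
| 470 | yes | no | yes | no |

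The overlap is 450 to 470 msec in women and the single value 450 in men. It touches one row of five.

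**2. Chance that a stable subject is counted, no drug effect**

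The Schedule of Activities has six post-dose ECGs (40 min, 2 h, 4 h, 6 h, 7 days, 14 days). For a stable QTcF *m* and independent reading error with SD *s* (assumed 5 to 12 msec), the chance of at least one value of 450 or more is 1 − Φ((450 − *m*)/*s*)^6.

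- *m* = 450: 1 − 0.5^6 = 98%.
- *m* = 455: 99.8% to 100%.
- *m* = 460 to 470: about 100%.
- *m* = 440: 13% (*s* = 5) to 74% (*s* = 12).

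The last line matters for the fix: subjects below 450 msec also cross by random variation.

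**3. How many subjects start at or above 450 msec**

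Assumptions, none from the documents: women's mean QTcF 415 or 425 msec; between-subject and within-subject SD 15 and 6, or 18 and 9; 50% or 65% women. The SD of one reading is √(15² + 6²) = 16.16 or √(18² + 9²) = 20.12. Truncating the baseline reading at 470 msec, with *a* = P(reading ≥ 450) and *b* = P(reading > 470), the share of eligible women at or above 450 is *p* = (*a* − *b*)/(1 − *b*). The expected number per arm is 31 × share of women × *p*.

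| Mean | SD | *a* | *b* | *p* | Per arm, 50% women | Per arm, 65% women |
|---|---|---|---|---|---|---|
| 415 | 16.16 | 0.0151 | 0.0003 | 0.0148 | 0.23 | 0.30 |
| 415 | 20.12 | 0.0410 | 0.0031 | 0.0380 | 0.59 | 0.77 |
| 425 | 16.16 | 0.0609 | 0.0027 | 0.0584 | 0.90 | 1.18 |
| 425 | 20.12 | 0.1071 | 0.0127 | 0.0956 | 1.48 | 1.93 |

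The range is about 0.2 to 2 per arm. Five of the eight values are below one, and all three above one need the higher assumed mean. Treating two arms as independent binomials of size 31, the chance that they differ by two or more such subjects is 4% at the lowest setting and 42% at the highest.

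In no-drug-effect simulations over similar ranges (men's mean 405 to 412 msec), 73% to 92% of subjects with a baseline of 450 or more were counted post-dose, and they made up 19% to 44% of everyone counted.

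**4. What this leaves out**

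Protocol 8.2.4 has abnormal ECGs repeated, and SAP VIII.G then analyses only the repeat. If every reading of 450 or more were repeated once (an assumption), the total counted falls from about 2–17% of subjects to 1–8%, and the share with a high baseline rises to about half. The 19–44% is therefore not firm in either direction.

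**The case against.** The strongest reply is that this is one descriptive row with no test attached, that no decision rule in the documents uses it, and that most of the context is already planned. QTcF values and changes are summarised by arm from baseline onward, with Q3 and maximum among the default statistics (SAP V.I). The baseline maximum in each arm will therefore show whether anyone started at 450 msec or more. Sex is tabulated by arm and all ECG measures are listed. Whether to count any post-baseline value or only new occurrences, pooled or by sex, is a presentation choice, and the documents require neither form for ECG. All of this stands, and it sets the priority low. What it does not supply is the number per arm already at or above 450 msec, or any count that excludes them.

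Three stronger readings are tempting and are not supported:

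- A reader might infer that the row biases the drug-placebo comparison. Randomization spreads high baselines over all arms on average, so only chance imbalance remains.
- A reader might infer that the SAP's QTcF analysis ignores baseline. Two of the five rows are changes from baseline, and two more lie above both entry limits.
- A reader might take one or two affected subjects per arm as an expected result. The documents give no QTcF mean, SD or sex mix, and most of the assumed settings give fewer than one.

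The reply also says that the fix is partial. That is correct: if 19% to 44% of those counted without a drug effect had a high baseline, the other 56% to 81% crossed from below.

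**Conclusion.** The mismatch is certain from the text: the lowest absolute row reports as prolonged an eligible woman whose QTcF stays anywhere from 450 to 470 msec. Its consequence is an inflated rate in each arm, with possible chance imbalance between arms of 31. It has no bearing on efficacy or on the other four QTcF rows, and for men it concerns only the value 450. The size cannot be derived from the documents. The 0.2 to 2 subjects per arm rests entirely on the assumed means, SDs and sex mix, on a single truncated baseline reading, and on ignoring the repeat-ECG rule. This is a low-priority improvement to safety reporting, worth making because it is almost free.

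**What to change.** In SAP VIII.G, keep the all-subject row for 450 msec or more and add, by arm and by sex:

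- (a) the number with a baseline QTcF of 450 msec or more, using the SAP V.B baseline. That value is normally the predose ECG and can differ from the screening and Day -1 values that decided eligibility;
- (b) a treatment-emergent count: baseline below 450 msec and at least one retained post-baseline value of 450 msec or more, with subjects below 450 msec at baseline as the denominator.

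Add a note that row (b) removes carried-in baseline values but not random crossings by subjects just under 450 msec, so it should be read against placebo. The 480, 500, 30 and 60 msec rows need no change.

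The cost is a few lines of SAP text and table programming. Baseline QTcF and sex are already collected, SAP I.B allows changes until database lock, and no procedure or eligibility rule is affected.

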2.3 Benefit/Risk Assessment

Due to its 4-fold lower affinity to the receptor, it is hypothesized that R-ketamine may have fewer N-methyl-D-aspartate receptor (NMDAR)-related adverse effects compared with racemic ketamine or S-ketamine, such as psychotomimetic effects and dissociation.

[REDACTED] It has been suggested that this action of R-ketamine may play a role in the hallucinogenic effects of racemic ketamine and that it may be responsible for the lowering of the seizure threshold seen with racemic ketamine.

Reported AEs from limited academic clinical studies in healthy volunteers evaluating R-ketamine subanesthetic doses of up to 1 mg/kg IV as bolus or short infusion or 1.8 mg/kg intramuscular included transient increases in blood pressure, emotional changes, illusion, sedation, proprioceptive and sensory disturbances, decline in concentration capacity and primary memory, blurred vision, altered hearing, and dizziness. Overall, less pronounced psychotomimetic and dissociative-like effects were reported with R-ketamine than with S-ketamine (20, 21, 22, 23, 24, 25). Results from an open-label pilot study of a single IV infusion of R-ketamine (0.5 mg/kg) administered to 7 subjects with TRD suggested that R-ketamine might produce fast-onset and sustained antidepressant effects with a favorable safety profile (35).

To date, there has been 1 clinical trial that evaluated the safety of PCN-101. The primary objective of study PCN-101-02 was to identify an acceptable tolerated dose of PCN-101 in healthy subjects and compare this dose to the safety profile of 15 mg S-ketamine, a dose which demonstrated a robust antidepressant effect in a published study of TRD patients (36). Dose ranging using single ascending doses of PCN-101-02 demonstrated that doses of PCN-101 \leq 150 mg had acceptable safety profiles as single 40-minute IV infusions. A comparison of the safety of dose levels of PCN-101 and 15 mg S-ketamine identified 60 mg PCN-101 as the dose level most similar to 15 mg S-ketamine in terms of safety profile. Both 30 mg and 60 mg doses of PCN-101 resulted in fewer transient elevations in mean systemic blood pressure, less sedation, fewer psychological or psychotic and dissociative effects, and fewer episodes of altered consciousness than 100 mg or 150 mg doses of PCN-101.

More detailed information about the known and expected benefits and risks and reasonably expected AEs of PCN-101 may be found in the current Investigator's Brochure.

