For chemistry, hematology, and urinalysis, any laboratory abnormalities will be listed separately. The abnormal laboratory listing will provide the entire profile for each subject and parameter with an abnormal post-baseline result.

E. Vital Signs and Pulse Oximetry

For vital signs (systolic and diastolic blood pressure, tympanic/temporal temperature, pulse, respiratory rate) and pulse oximetry, summaries of actual values and changes from baseline will be presented by treatment group for each scheduled assessment timepoint, beginning with the Baseline visit. For this analysis, any lab collection performed on unscheduled analysis visits will not be summarized, with the exception of the inclusion of unscheduled pre-dose assessments used in the classification of baseline, as described in [Section V.B Definition of Baseline](#).

Vital signs will consist of three (3) blood pressure measurements (recorded at intervals of at least 1 minute). The arithmetic mean of the three (3) blood pressure readings will be recorded in the CRF and used for this analysis.

Temperature data collected via tympanic or temporal methods will be pooled for analysis.

The incidence of clinically relevant abnormality will be summarized by treatment. For this analysis, any unscheduled post-baseline records will be included for assessment. A listing of clinically relevant abnormality vital signs will be displayed.

Table 4 Potential Clinically Relevant Abnormalities in Vital Signs

Parameter	Unit	Low	High
Systolic blood pressure	mmHg	≤ 90 or CFB ≤ -20	≥ 180 or CFB ≥ 20
Diastolic blood pressure	mmHg	≤ 50 or CFB ≤ -15	≥ 105 or CFB ≥ 15
Pulse	beats/min	≤ 50 or CFB ≤ -15	≥ 120 or CFB ≥ 15
Temperature	°C	CFB ≤ -2	≥ 38.3 or CFB ≥ 1.1
Respiratory Rate	breaths/min	<8	Not applicable
Oxygen Saturation	%	< 90%	Not applicable

CFB = change from Baseline.

All vital signs data will be listed

F. Physical Examination

All physical examination results will be listed by subject.

G. Electrocardiograms

12-Lead ECGs will be obtained using an ECG machine that automatically calculates the parameters for analysis. If abnormal, the ECG needs to be repeated.

An overall interpretation of the ECG results, PR intervals, RR intervals, QT uncorrected intervals, QT intervals corrected by Fridericia's formula (QTcF) will be listed by subject.

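### The QTcF and vital-sign abnormality tables count crossings over one window to Day 15, so no planned table counts subjects who crossed a limit around the infusion

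*SAP*

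**What the plan says.** SAP VIII.G (Electrocardiograms) plans a count of subjects reaching absolute QTcF limits of 450, 480 and 500 msec and increases of 30 and 60 msec: "A separate summary table will provide the number and percentage of subjects meeting the following criteria post-baseline". Unscheduled tracings are included: "For this analysis, any ECG performed on unscheduled analysis visits will be included for analysis". Where a subject has abnormal ECG interpretations of differing clinical significance "at different analysis timepoints in a post-baseline period, the most severe record" is used. If an ECG is repeated, "only the second (repeat) measure will be included for analysis and the first measure will not be analyzed".

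SAP VIII.E (Vital Signs and Pulse Oximetry) says: "The incidence of clinically relevant abnormality will be summarized by treatment", and then: "For this analysis, any unscheduled post-baseline records will be included for assessment". It names no timepoint for this count, although the continuous summaries in the same section are given per scheduled timepoint. Its Table 4 limits include changes from baseline of 20 mmHg systolic, 15 mmHg diastolic and 15 beats/min.

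The protocol's Schedule of Activities (1.3) places post-dose ECGs at end of infusion, 2, 4 and 6 h, Day 8 and Day 15. Vital signs follow the same times plus 24 h. SpO2 is monitored only to 4 h.

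**The concern.** With one infusion on Day 1, a drug effect on blood pressure, pulse or QTcF is most likely in the first hours. Protocol 2.3 treats the blood-pressure effect as short-lived: in Phase 1 the two study doses "resulted in fewer transient elevations in mean systemic blood pressure" than the higher doses. A reading one or two weeks later mainly reflects day-to-day variation against a single predose baseline. If it crosses a limit, the subject enters the same cell as one whose pressure rose at end of infusion.

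These late crossings arise at similar rates in all arms. They raise every percentage and pull the arms together. A subject who already crossed on Day 1 cannot be counted twice, so the arm with more acute crossings gains fewer late ones. At stake is a plain safety figure: how many subjects per arm crossed a limit around the infusion. It bears on the comparison of 30 mg with 60 mg and on the aim of at-home use. No planned table gives it.

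**Working it through.** **Inputs from the documents.** Late readings (24 h or later): 3 of 7 vital-sign sets and 2 of 6 ECGs (Schedule of Activities). Limits: SAP Table 4 and VIII.G. Arm size: 31 (SAP III.C). The plan states no expected rate for these tables, so it has no figure to reproduce here. Its 80% power concerns the MADRS.

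**Assumed, because the documents give no values.** Reading SDs, between-day SDs and the size of the acute rise.

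**Step 1: direction.** Let A be the probability of crossing acutely and q the chance of crossing at one late reading, with no late drug effect and k independent late readings. The any-time rate is A + (1 − A)[1 − (1 − q)^k]. Subtracting placebo from active multiplies the acute risk difference by (1 − q)^k.

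- Two late readings (ECG): 0.998 at q = 0.1%, 0.96 at 2%, 0.90 at 5%, 0.81 at 10%.
- Three late readings (vital signs): at q = 5%, 0.95³ = 0.86.

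Any q above zero dilutes the difference. If q is near zero, nothing is lost.

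**Step 2: diastolic change of 15 mmHg or more.** Baseline b ~ N(0, s²). There are four acute readings with SD s and true rises on active of 8, 2.4, 0 and 0 mmHg, and three late readings with no drug effect and SD √(s² + d²). Given b, the probability of never crossing is ∏Φ((15 + b − rise)/s) over the acute readings, times Φ((15 + b)/√(s² + d²))³ for the late ones. Averaging over b numerically gives, in percent (acute → any time):

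| s | d | Placebo | Active | Difference (points) | Share of difference lost | Loss × 31 |
|---|---|---|---|---|---|---|
| 3 | 0 | 0.08 → 0.13 | 5.04 → 5.06 | 4.96 → 4.93 | 0.6% | 0.01 |
| 3 | 4 | 0.08 → 1.53 | 5.04 → 6.12 | 4.96 → 4.60 | 7% | 0.11 |
| 4 | 0 | 1.41 → 2.25 | 11.69 → 12.07 | 10.28 → 9.82 | 4% | 0.14 |
| 4 | 4 | 1.41 → 5.16 | 11.69 → 14.08 | 10.28 → 8.92 | 13% | 0.42 |
| 6 | 0 | 11.48 → 16.48 | 25.76 → 28.51 | 14.29 → 12.03 | 16% | 0.70 |
| 6 | 4 | 11.48 → 19.86 | 25.76 → 30.90 | 14.29 → 11.04 | 23% | 1.01 |
| 8 | 0 | 24.27 → 32.60 | 37.14 → 42.30 | 12.88 → 9.70 | 25% | 0.98 |
| 8 | 4 | 24.27 → 34.95 | 37.14 → 44.07 | 12.88 → 9.12 | 29% | 1.17 |

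For s = 6, d = 4: 14.29 − 11.04 = 3.25 points; 3.25/14.29 = 23%; 0.0325 × 31 = 1.01 subjects. A simulation of this model put the range at about 0.5% to 28%, the same within simulation error. If 24 h is not counted as late, the s = 6 losses become 11% and 16%.

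**Step 3: other rows.** A separate simulation treated only Days 8 and 15 as late and used other assumed SDs. The share of the acute difference kept was:

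- systolic 20: 0.69 to 0.94 (between-day SD 4–10, within-day SD 5–8 mmHg);
- pulse 15: 0.69 to 0.83;
- QTcF 30: 0.76 to 0.95 (between-day SD 5–9, within-day SD 6–10 msec).

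In the noisiest systolic case with the larger assumed effect, the difference fell from 26.9 to 19.4 points (0.075 × 31 = 2.3 subjects). For QTcF change of 60 msec or more, late chance crossings occurred in 0 to 0.15% of subjects, so that row does not move. With QTcF reading SD 10 msec, no between-day component and no drug effect, the 30 msec background rises from 5.5% to 7.4%, or 0.6 of a subject in 31.

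**The case against.** The case for leaving the tables alone is substantial.

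- **Acute effects remain visible elsewhere.** SAP V.I makes quartiles and extremes part of the default continuous summary, and VIII.E and VIII.G apply summaries of values and changes at each scheduled timepoint. The upper quartile and maximum of the end-of-infusion change show whether about a quarter of an arm, or anyone, passed a limit. There is also a listing of abnormal vital signs, and listings are ordered by assessment time, so at 31 per arm a Day 1 count could be made by hand. This stands as partial mitigation, but it is not a planned count.
- **Chance crossings are already limited.** Blood pressure is the mean of three readings, which favours the lower SDs above. The ECG repeat rule removes some chance QTcF crossings. Both points stand.
- **The loss is small against sampling error.** At s = 6 the acute difference has a standard error of √(0.115 × 0.885/31 + 0.258 × 0.742/31), about 10 points, against a loss of 2 to 3 points. Acute readings also cross by chance: 11.5% on placebo in that model, which a time split leaves in place.

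A reader might infer that both tables are distorted throughout, or that any limit would be diluted to a degree that matters. The documents do not support this: SpO2 has no scheduled late readings, and rare limits barely move. A reader might also infer that the tables exist to compare acute effects. Neither SAP section says so, and an any-time count is a reasonable catch-all for delayed events. Nor does the transience wording extend to QTcF; it concerns mean blood pressure.

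**Conclusion.** The point holds as a minor improvement to a descriptive display. The single window is explicit for QTcF and is the natural reading for vital signs, and no planned table counts crossings around the infusion. For the four low change-from-baseline limits the dilution runs one way. In the diastolic model it takes about 0.6% to 29% of the acute difference, about one subject or fewer per arm of 31; the noisiest systolic case reaches about two.

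These sizes rest on assumed SDs and rises, on no drug effect at 24 h or later, and on classing 24 h as late. The direction needs only the absence of a late drug effect and some chance of a late crossing. No hypothesis test, error rate or decision rule depends on these tables, and the late readings are not wrong to count.

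**What to change.** Before database lock, while SAP I.B still allows changes, add two sets of rows to both tables, using the same limits:

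- end of infusion to 6 h, with unscheduled Day 1 readings;
- follow-up: 24 h to Day 15 for vital signs, and Days 8 and 15 for ECGs, with unscheduled readings after Day 1.

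Keep the any-time count as the total, so that a delayed event is still captured. State in VIII.E that the existing incidence is an any-time count.

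The change needs SAP wording and a grouping variable in two existing tables, and no new data. Its downside is slightly longer output. Fixing the periods before unblinding also avoids choosing them after the results are seen.
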